#### Clinical efficacy

Efficacy as monotherapy has been evaluated in one randomised, double-blind, placebo-controlled study lasting 2 years (AFFIRM study) in relapsing-remitting MS patients who had experienced at least 1 clinical relapse during the year prior to entry and had a Kurtzke Expanded Disability Status Scale (EDSS) score between 0 and 5. Median age was 37 years, with a median disease duration of 5 years.

The patients were randomised with a 2:1 ratio to receive TYSABRI 300 mg (n = 627) or placebo (n = 315) every 4 weeks for up to 30 infusions. Neurological evaluations were performed every 12 weeks and at times of suspected relapse. MRI evaluations for T1-weighted gadolinium (Gd)-enhancing lesions and T2-hyperintense lesions were performed annually. Study features and results are presented in the table below.

AFFIRM study: Main features and results		
Design	Monotherapy; randomised double-blind placebo-controlled parallel-group trial for 120 weeks	
Subjects	RRMS (McDonald criteria)	
Treatment	Placebo / Natalizumab 300 mg i.v. every 4 weeks	
One year endpoint	Relapse rate	
Two year endpoint	Progression on EDSS	
Secondary endpoints	Relapse rate derived variables / MRI-derived variables	
Subjects	Placebo	Natalizumab
Randomised	315	627
Completing 1 years	296	609
Completing 2 years	285	589
Age yrs, median (range)	37 (19-50)	36 (18-50)
MS-history yrs, median (range)	6.0 (0-33)	5.0 (0-34)
Time since diagnosis, yrs median (range)	2.0 (0-23)	2.0 (0-24)
Relapses in previous 12 months, median (range)	1.0 (0-5)	1.0 (0-12)
EDSS-baseline, median (range)	2 (0-6.0)	2 (0-6.0)
RESULTS		
Annual relapse rate		
After one year (primary endpoint)	0.805	0.261
After two years	0.733	0.235
One year	Rate ratio 0.33 CI 95% 0.26 ; 0.41	
Two years	Rate ratio 0.32 CI 95% 0.26 ; 0.40	
Relapse free		
After one year	53%	76%
After two years	41%	67%
Disability		
Proportion progressed  (12-week confirmation; primary outcome)	29%	17%
	Hazard ratio 0.58, CI 95% 0.43; 0.73, p<0.001	
Proportion progressed  (24-week confirmation)	23%	11%
	Hazard ratio 0.46, CI 95% 0.33; 0.64, p<0.001	
MRI (0-2 years)		
Median % change in T2-hyperintense lesion volume	+8.8%	-9.4% (p<0.001)
Mean number of new or newly-enlarging T2-hyperintense lesions	11.0	1.9 (p<0.001)
Mean number of T1-hypointense lesions	4.6	1.1 (p<0.001)
Mean number of Gd-enhancing lesions	1.2	0.1 (p<0.001)
 Progression of disability was defined as at least a 1.0 point increase on the EDSS from a baseline EDSS ≥1.0 sustained for 12 or 24 weeks or at least a 1.5 point increase on the EDSS from a baseline EDSS =0 sustained for 12 or 24 weeks.		

In the sub-group of patients indicated for treatment of rapidly evolving relapsing remitting MS (patients with 2 or more relapses and 1 or more Gd+ lesion), the annualised relapse rate was 0.282 in the TYSABRI treated group (n = 148) and 1.455 in the placebo group (n = 61) (p <0.001). Hazard ratio for disability progression was 0.36 (95% CI: 0.17, 0.76) p = 0.008. These results were obtained from a *post hoc* analysis and should be interpreted cautiously. No information on the severity of the relapses before inclusion of patients in the study is available.

The European Medicines Agency has deferred the obligation to submit the results of studies with TYSABRI in one or more subsets of the paediatric population in multiple sclerosis (see section 4.2 for information on paediatric use).

## 5.2 Pharmacokinetic properties

Following the repeat intravenous administration of a 300 mg dose of natalizumab to MS patients, the mean maximum observed serum concentration was  $110 \pm 52$  µg/ml. Mean average steady-state trough natalizumab concentrations over the dosing period ranged from 23 µg/ml to 29 µg/ml. The predicted time to steady-state was approximately 36 weeks.

A population pharmacokinetics analysis was conducted on samples from over 1,100 MS patients receiving doses ranging from 3 to 6 mg/kg natalizumab. Of these, 581 patients received a fixed 300 mg dose as monotherapy. The mean  $\pm$  SD steady-state clearance was  $13.1 \pm 5.0$  ml/h, with a mean  $\pm$  SD half-life of  $16 \pm 4$  days. The analysis explored the effects of selected covariates including body weight, age, gender, hepatic and renal function, and presence of anti-natalizumab antibodies upon pharmacokinetics. Only body weight and the presence of anti-natalizumab antibodies were found to influence natalizumab disposition. Body weight was found to influence clearance in a less-than-proportional manner, such that a 43% change in body weight resulted in a 31% to 34% change in clearance. The change in clearance was not clinically significant. The presence of persistent anti-natalizumab antibodies increased natalizumab clearance approximately 3-fold, consistent with reduced serum natalizumab concentrations observed in persistently antibody-positive patients, (see section 4.8).

The pharmacokinetics of natalizumab in paediatric MS patients or in patients with renal or hepatic insufficiency has not been studied.

The effect of plasma exchange on natalizumab clearance and pharmacodynamics was evaluated in a study of 12 MS patients. Estimates of the total natalizumab removal after 3 plasma exchanges (over a 5-8 day interval) was approximately 70-80%. This compares to approximately 40% seen in earlier studies in which measurements occurred after natalizumab discontinuation over a similar period of observation. The impact of plasma exchange on the restitution of lymphocyte migration and ultimately its clinical usefulness is unknown.

## 5.3 Preclinical safety data

Non-clinical data reveal no special hazard for humans based on conventional studies of safety pharmacology, repeated dose toxicity and genotoxicity.

Consistent with the pharmacological activity of natalizumab, altered trafficking of lymphocytes was seen as white blood cell increases as well as increased spleen weights in most *in vivo* studies. These changes were reversible and did not appear to have any adverse toxicological consequences.

In studies conducted in mice, growth and metastasis of melanoma and lymphoblastic leukaemia tumour cells was not increased by the administration of natalizumab.

No clastogenic or mutagenic effects of natalizumab were observed in the Ames or human chromosomal aberration assays. Natalizumab showed no effects on *in vitro* assays of  $\alpha$ 4-integrin-positive tumour line proliferation or cytotoxicity.

Reductions in female guinea pig fertility were observed in one study at doses in excess of the human dose; natalizumab did not affect male fertility.

The effect of natalizumab on reproduction was evaluated in 5 studies, 3 in guinea pigs and 2 in *cynomolgus* monkeys. These studies showed no evidence of teratogenic effects or effects on growth of offspring. In one study in guinea pigs, a small reduction in pup survival was noted. In a study in monkeys, the number of abortions was doubled in the natalizumab 30 mg/kg treatment groups versus matching control groups. This was the result of a high incidence of abortions in treated groups in the first cohort that was not observed in the second cohort. No effects on abortion rates were noted in any other study. A study in pregnant *cynomolgus* monkeys demonstrated natalizumab-related changes in the foetus that included mild anaemia, reduced platelet counts, increased spleen weights and reduced liver and thymus weights. These changes were associated with increased splenic extramedullary haematopoiesis, thymic atrophy and decreased hepatic haematopoiesis. Platelet counts were also reduced in offspring born to mothers treated with natalizumab until parturition, however there was no evidence of anaemia in these

offspring. All changes were observed at doses in excess of the human dose and were reversed upon clearance of natalizumab.

In *cynomolgus* monkeys treated with natalizumab until parturition, low levels of natalizumab were detected in the breast milk of some animals.

## **6. PHARMACEUTICAL PARTICULARS**

### **6.1 List of excipients**

Sodium phosphate, monobasic, monohydrate  
Sodium phosphate, dibasic, heptahydrate  
Sodium chloride  
Polysorbate 80 (E433)  
Water for injections

### **6.2 Incompatibilities**

TYSABRI must not be mixed with other medicinal products except those mentioned in section 6.6.

### **6.3 Shelf life**

Unopened vial 4 years

Diluted solution

After dilution with sodium chloride 9 mg/ml (0.9%) solution for injection, immediate use is recommended. If not used immediately, the diluted solution must be stored at 2°C - 8°C and infused within 8 hours of dilution. In-use storage times and conditions prior to use are the responsibility of the user.

### **6.4 Special precautions for storage**

Store in a refrigerator (2°C - 8°C).

Do not freeze.

Keep the vial in the outer carton in order to protect from light.

For storage conditions after dilution of the medicinal product see section 6.3.

### **6.5 Nature and contents of container**

15 ml concentrate in a vial (type I glass) with a stopper (bromobutyl rubber) and a seal (aluminium) with a flip-off cap.

Pack size of one vial per carton.

### **6.6 Special precautions for disposal and other handling**

Instructions for use:

- Inspect the TYSABRI vial for particles prior to dilution and administration. If particles are observed and/or the liquid in the vial is not colourless, clear to slightly opalescent, the vial must not be used.
- Use aseptic technique when preparing TYSABRI solution for intravenous (IV) infusion. Remove flip-off cap from the vial. Insert the syringe needle into the vial through the centre of the rubber stopper and remove 15 ml concentrate for solution for infusion.
- Add the 15 ml concentrate for solution for infusion to 100 ml sodium chloride 9 mg/ml (0.9%) solution for injection. Gently invert the TYSABRI solution to mix completely. Do not shake.
- TYSABRI must not be mixed with other medicinal products or diluents.
- Visually inspect the diluted medicinal product for particles or discolouration prior to administration. Do not use if it is discoloured or if foreign particles are seen.

- The diluted medicinal product is to be used as soon as possible and within 8 hours of dilution. If the diluted medicinal product is stored at 2°C - 8°C (do not freeze), allow the solution to warm to room temperature prior to infusion.
- The diluted solution is to be infused intravenously over 1 hour at a rate of approximately 2 ml/minute.
- After the infusion is complete, flush the intravenous line with sodium chloride 9 mg/ml (0.9%) solution for injection.
- Each vial is for single-use only.
- Any unused medicinal product or waste material must be disposed of in accordance with local requirements.

#### **8. MARKETING AUTHORISATION NUMBER(S)**

EU/1/06/346/001

#### **9. DATE OF FIRST AUTHORISATION/RENEWAL OF THE AUTHORISATION**

Date of first authorisation: 27th June 2006  
Date of latest renewal:

#### **10. DATE OF REVISION OF THE TEXT**

Detailed information on this medicinal product is available on the website of the European Medicines Agency <http://www.ema.europa.eu>.

Multiple sclerosis (MS) is a chronic, inflammatory, demyelinating, and degenerative disease of the central nervous system (CNS) that affects approximately 400,000 people in the United States (U.S.) and 2.3 million worldwide ([Tullman et al. 2013](#)). MS is clinically subcategorized into four phenotypic disease patterns distinguished by the occurrence and timing of relapses relative to disease onset and disability progression. These include relapsing remitting MS (RRMS), primary progressive MS (PPMS), progressive relapsing MS (PRMS), and secondary progressive MS (SPMS) ([Lublin et al. 1996](#), [Lublin et al. 2014](#)). Accumulated disability is the fate of most patients with MS when a 20- to 25-year perspective is considered ([Trojano et al. 2003](#)). Approximately 85% of MS patients initially present with RRMS ([Confavreaux et al. 2000](#); [Leray et al. 2015](#)).

Over the past two decades, there has been an increase in the number and type of available treatments for relapsing multiple sclerosis (RMS). Assessing efficacy and safety in patients who switch to ocrelizumab after a suboptimal response to an adequate course of a disease modifying therapy (DMT) represents an important question for clinicians. Efficacy and safety data in patients who have switched to ocrelizumab are limited. Additional data will also be available on previously treated patients in two completed Phase III studies (NCT01247324 [OPERA I], n=106 and NCT01412333 [OPERA II], n=113), but in a limited number of patients. However, more data from patients who switch to higher efficacy therapies from large scale, prospective studies are needed. Therefore, a dedicated prospective study to specifically evaluate the efficacy and safety of ocrelizumab in patients who have a suboptimal response to an adequate course of a DMT is needed to address this important clinical question.

Please refer to the protocol for the references cited above and for further details on ocrelizumab background.

2. **STUDY DESIGN**

This study is a prospective, multicenter, open-label, efficacy and safety study in patients with RRMS who have had a suboptimal response to an adequate course of a DMT. An adequate course of prior DMT is defined as a stable dose of the same DMT administered for at least 6 months. The first dose of ocrelizumab will be administered as an initial dose of two 300-mg infusions (600 mg total) in 250 mL 0.9% sodium chloride each separated by 14 days (i.e., Days 1 and 15) followed by one 600-mg infusion in 500 mL 0.9% sodium chloride every 24 weeks for the remainder of the study duration.

This study will enroll approximately 750 patients. Patients will be assessed for efficacy and safety every 24 weeks as described in the Schedule of Assessments in [Appendix 2](#).

The study will consist of the following periods:

- Screening period: Up to 4 weeks
- Treatment period: Open-label treatment period of 96 weeks (last dose administered at Week 72)
- A follow-up period of at least 2 years, which is independent of the DMT administered

Follow-up Period: Patients who discontinue treatment early will be followed up for at least 96 weeks after the Early Treatment Discontinuation Visit. Patients who complete the 96 weeks Treatment Period and, in agreement with their treating neurologist, decide not to continue in a separate long term extension (LTE) study, will be followed up for at least 96 weeks after the end of the Treatment Period. Patients who decide to leave the study and switch to commercially marketed ocrelizumab, either after completion of the 96 weeks Treatment Period or after early discontinuation of the 96 weeks Treatment Period, will not enter the safety Follow-up Period.

2.1 PROTOCOL SYNOPSIS

The Protocol Synopsis is in [Appendix 1](#). For additional details, see the Schedule of Assessments in [Appendix 2](#).

2.2 OUTCOME MEASURES

2.2.1 Primary Efficacy Outcome Measures

The primary efficacy endpoint is the proportion of patients who have No Evidence of Disease Activity (NEDA), as per protocol defined events during a 96-week period. The magnetic resonance imaging (MRI) activity will be calculated on the events starting from week 8 (baseline reset).

The definition of a protocol-defined event of disease activity is defined in Section [4.4.1](#)

2.2.2 Secondary Efficacy Outcome Measures

The secondary efficacy endpoints are the following:

- Proportions of NEDA patients during the initial 24-week period and the initial 48-week period
- Time to first protocol-defined event of disease activity
- Change in EDSS from baseline to Week 96
- Proportion of patients who, over a 96-week period, have Confirmed Disability Improvement (CDI), CDP or stable disability (i.e. neither CDI nor CDP).
- Annualized rate of protocol-defined relapses at Week 96
- Time to onset of first protocol-defined relapse
- Time to onset of 24 weeks CDP
- Time to onset of first new and/or enlarging T2 lesion
- Total number of T1 Gd-enhanced lesions detected by brain MRI at Weeks 24, 48 and 96

- Change in total T2 lesion volume detected by brain MRI from Week 8 to Week 96
- Volume and number of new and/or enlarging T2 hyperintense lesions from Week 8 to Weeks 24, 48 and 96
- Change in T1 hypointense lesion volume from Week 8 to Weeks 48 and 96
- Percentage change in brain volume from Week 8 measured at Weeks 24, 48 and 96
- Percentage change in white matter volume from Week 8 measured at Weeks 24, 48 and 96
- Percentage change in cortical grey matter volume from Week 8 measured at Weeks 24, 48 and 96
- Change from baseline in cognitive performance at Week 48 and Week 96 as measured by the components of the Brief International Cognitive Assessment for Multiple Sclerosis (BICAMS)

2.2.3 Exploratory Outcome Measures

Exploratory outcome measures are used to further assess the efficacy of ocrelizumab 600 mg IV administered every 24 weeks. These include:

- Multiple Sclerosis Impact Scale version 2 (MSIS-29 v2)
- Treatment satisfaction questionnaire for medication (TSQM II)
- SymptoMScreen
- Work Productivity and Activity Impairment (WPAI-SHP) to assess the employment status
- MRI and clinical outcomes
- Severity of relapses (hospitalization for MS relapse, use of corticosteroids, residual disability)
- NEDA status of patients defined from per protocol defined events during a 96-week period and starting from baseline (not from baseline reset week 8)
- Predictors of NEDA and association between NEDA and disability or other efficacy parameters
- NEDA in Year 1 (from Weeks 0/8 to Week 48) and NEDA in Year 2 (from Week 48 to Week 96) by epoch

2.2.4 Pharmacokinetic Efficacy Outcome Measures

Not Applicable

2.2.5 Safety Outcome Measures

The safety and tolerability endpoints are:

- Rate and severity of adverse events
- Changes in vital signs, physical and neurological examinations, clinical laboratory results, locally reviewed MRI for safety (non-MS CNS pathology) and concomitant medications (including pre-medications and medications used during and following ocrelizumab administration).

2.3 DETERMINATION OF SAMPLE SIZE

With a sample size of 750 patients, an observed NEDA rate of 30% will be estimated with a precision (half-width of the 95% CI (Confidence Interval) around the estimate) of 3.3% based on the Clopper-Pearson method, i.e. the 95% CI will be (26.7%, 33.4%). Even if the NEDA rate is different from the assumed rate of 30%, with the proposed sample size the precision of the estimate will remain better than 3.6% (value for a NEDA rate of 50%).

The annualized relapse rate is another relevant outcome measure assessed in this study. Based on results from the pivotal Phase III studies NCT01247324 (OPERA I) and NCT01412333 (OPERA II), in this study the adjusted annualized relapse rate (ARR) assessed over two years is expected to be estimated with a precision of approximately 0.03.

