4.1.2 Modified ITT population

The modified intention-to-treat (mITT) population will be defined as all patients from the ITT population excluding patients with both the screening and the baseline EDSS scores missing.

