4.4 EFFICACY ANALYSIS

4.4.1 Primary Efficacy Endpoint

Protocol-defined event definition

The definition of a protocol-defined event of disease activity is the occurrence of at least one of the following individual events while on treatment with ocrelizumab:

- A protocol-defined relapse defined as an occurrence of new or worsening neurological symptoms attributable to MS. Symptoms must persist for > 24 hours and should not be attributable to confounding clinical factors (e.g., fever, infection, injury, adverse reactions to medications), and immediately be preceded by neurological stability for at least 30 days.
- 24-weeks CDP based on increase in EDSS while on treatment with ocrelizumab
- A new T1 Gd-enhanced lesion on MRI after week 8
- A new and/or enlarging T2 hyperintense lesion on MRI after week 8

The MRI activity will be calculated on the events starting from week 8 (baseline reset).

Patient without any of this protocol-defined event of disease activity will be considered as NEDA = Yes (no evidence of disease activity).

The primary endpoint, NEDA, as well as the related disease activities components and combinations listed below, will be evaluated on the mITT population based on the following analysis principles:

- Patients, who discontinued treatment prior week 96 due to death or lack of efficacy, will be considered as having evidence of disease activity at the time of treatment discontinuation (e.g NEDA="NO", Relapse="Yes" and CDP="Yes").
- Patients who discontinued treatment for reasons other than death or lack of efficacy with no evidence of disease activity at the time of early treatment discontinuation will be excluded from the analysis as their disease activity status cannot be ascertained.

This is further summarized in the table below:

Endpoint	Patients who discontinued treatment without related disease activities prior week 96 due to:	
	death or lack of efficacy	Other reason than death or lack of efficacy with no evidence of disease activity
NEDA	included with evidence of disease activity (NEDA=NO)	excluded
Relapse	included with evidence of disease activity (Relapse=Yes)	excluded

24-weeks CDP	included with evidence of disease activity (CDP="Yes")	
 • If discontinuation before confirmation, excluded • If discontinuation after confirmation, included when CDP="Yes"
T1 Gd-enhanced lesions after week 8	included with evidence of disease activity	excluded

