New/enlarging T2 lesions after week 8	included with evidence of disease activity	excluded

Analysis of binary NEDA

The proportions of patients with:

- NEDA
- Treatment discontinuation due to lack of efficacy or death without events prior the withdrawal
- Relapses
- No Relapse
- 24-weeks CDP
- No 24 weeks CDP
- T1 Gd-enhanced lesions after week 8
- No T1 Gd-enhanced lesions after week 8
- New/enlarging T2 lesions after week 8
- No New/enlarging T2 lesions after week 8
- MRI activity (T1 Gd-enhanced lesions or new/enlarging T2 lesions)
- No MRI activity
- Relapses or MRI activity
- 24-weeks CDP or MRI activity
- Clinical activity (Relapses or 24-weeks CDP)
- No clinical activity
- Relapses and MRI activity
- 24-weeks CDP and MRI activity
- Relapses and 24-weeks CDP

post-baseline up to the Week 96 visit will be calculated and presented with a two-sided 95% Clopper-Pearson exact confidence interval.

Protocol-Defined Relapse definition

A protocol-defined MS relapse is an occurrence of new or worsening neurological symptoms attributable to MS that meets the following criteria:

- Symptoms must persist for >24 hours and should not be attributable to confounding clinical factors (e.g., fever, infection, injury, adverse reactions to medications)
- Symptoms should be preceded by neurological stability for at least 30 days
- Symptoms should be accompanied by new objective neurological worsening determined with a timely EDSS/ Functional Systems Score (FSS) assessment, consistent with an increase of at least:
 - ≥ 0.5 points on EDSS scale
 - or ≥ 2 points on one of the following FSS scales: pyramidal, ambulation, cerebellar, brainstem, sensory, or visual
 - or ≥ 1 point on two or more of the following FSS scales: pyramidal, ambulation, cerebellar, brainstem, sensory, or visual

Information related to a PDR will be captured on a clinical relapse event case report form (CRF) page (Multiple Sclerosis Relapse). If the following criteria are satisfied, the clinical relapse will qualify as a PDR:

1. Clinical relapse is reported on eCRF.
2. Check-box of “Did symptoms persist for >24 hours and were not being attributable...” on the Clinical MS relapse event is checked.

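### The NEDA precision in SAP 2.3 is computed on all 750 patients, but the primary analysis excludes event-free discontinuers, and the exact worst case at 750 is already 3.64%

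*SAP*

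**What the plan says.** **Sizing.** SAP 2.3 and Protocol 6.1 size the study by precision. The SAP states: "With a sample size of 750 patients, an observed NEDA rate of 30% will be estimated with a precision" of 3.3%, "based on the Clopper-Pearson method, i.e. the 95% CI will be (26.7%, 33.4"%). For any other rate, "the precision of the estimate will remain better than 3.6% (value for a NEDA rate of 50"%). The synopsis in the protocol, repeated in SAP Appendix 1, makes the same claim with a near-identical phrase. The same section also cites an expected precision of about 0.03 for the adjusted annualized relapse rate. On enrolment, SAP section 2 says: "This study will enroll approximately 750 patients". No dropout allowance appears in either document.

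**Primary analysis.** SAP 4.4.1 says that NEDA and its components "will be evaluated on the mITT population based on the following analysis principles". The mITT set is the ITT set "excluding patients with both the screening and the baseline EDSS scores missing" (SAP 4.1.2). Patients who stop before Week 96 because of death or lack of efficacy are kept and counted as having disease activity. Those who stop for any other reason with no event so far "will be excluded from the analysis as their disease activity status cannot be ascertained". The proportion is then "presented with a two-sided 95% Clopper-Pearson exact confidence interval".

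**Related rules.** Protocol 4.6.2 does not replace patients who discontinue treatment. Protocol section 6 takes the ITT population for efficacy, but SAP section 4 says that its analyses take precedence over the protocol's.

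**The concern.** Two things do not fit together. First, the worst case is worded as a strict bound, and the exact interval named in the same sentence does not meet it even with all 750 patients. Second, the precision is worked out for 750 patients, while the SAP's own primary analysis removes a group from the denominator. The 750 figure suits the protocol's primary set, which is every treated patient. It was carried over into a SAP whose primary set is smaller.

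At stake is whether the stated precision describes the analysis that will be done. A reader who takes 3.3% and 3.6% as what the primary result will achieve would expect an interval slightly narrower than the one reported.

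**Working it through.** **Inputs.** n = 750, planning rate 30%, worst-case rate 50%, two-sided 95% Clopper-Pearson interval (SAP 2.3 and 4.4.1). The share of patients excluded as event-free discontinuers is not given, so it is an assumption, varied from 0% to 20%.

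**Formula.** With x patients with NEDA out of n, the lower limit L is the 2.5% quantile of Beta(x, n − x + 1), the upper limit U is the 97.5% quantile of Beta(x + 1, n − x), and the half-width is (U − L)/2.

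**Step 1: the plan's own figures.**

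- 30%: x = 225, n = 750. L = 26.74%, U = 33.42%, half-width (33.42 − 26.74)/2 = 3.34%. This matches the stated 3.3% and (26.7%, 33.4%).
- 50%: x = 375, n = 750. L = 46.36%, U = 53.64%, half-width (53.64 − 46.36)/2 = 3.64%. This is the largest value over all x. It agrees with 3.6% at one decimal but is not below it.

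Other interval formulas at 50% give 3.58% (Wald) and 3.57% (Wilson), which would satisfy the wording, but the plan names Clopper-Pearson.

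**Step 2: how much slack there is.** A half-width strictly below 3.60% at a 50% rate needs 767 analysed patients; 766 gives 3.600%. To round to 3.6%, at least 746 of 750 must be analysed. With 745, a loss of 5/750 = 0.7%, the half-width is 3.651%, which rounds to 3.7%.

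**Step 3: half-width by assumed share excluded** (n and x rounded to whole patients).

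| Excluded (assumed) | n analysed | At 30% | At 50% |
|---|---|---|---|
| 0% | 750 | 3.34% | 3.64% |
| 2% | 735 | 3.37% | 3.68% |
| 3.5% | 724 | 3.40% | 3.70% |
| 5% | 712 | 3.43% | 3.74% |
| 10% | 675 | 3.52% | 3.84% |
| 15% | 638 | 3.63% | 3.95% |
| 20% | 600 | 3.74% | 4.08% |

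The 3.5% row uses the one related figure in the documents: the share stopping ocrelizumab for adverse events in the two earlier relapsing-MS trials (Protocol 1.2, Clinical Safety). It is not an estimate of this trial's exclusion rate.

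**Step 4: where the bound fails.** At n = 750 the half-width reaches 3.6% only for NEDA rates between 320/750 = 42.7% and 430/750 = 57.3%. At the 30% planning rate it stays below 3.6% down to about 648 analysed patients, that is until about 102/750 = 13.6% are excluded.

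**The case against.** The strongest reply is that this is rounding plus an assumed loss. The plan reports to one decimal, its figures reproduce at that precision, and only the claim to be better than 3.6% fails, by 0.04 percentage points. That is fair: a reader might infer a calculation error, and there is none.

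The sentence is also conditional on a sample of 750 and records a planning calculation made when the primary set was all treated patients. That explains the mismatch but does not remove it, because SAP 2.3 presents the precision of the NEDA estimate beside a primary analysis with a different denominator.

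The loss may be small. Only event-free discontinuers leave; with a planning NEDA rate of 30%, many discontinuers may already have had an event and so stay in. The mITT step should remove almost nobody, since a screening EDSS is required for entry (Protocol 4.1.1). Enrolment is approximate and could end slightly above 750. All of this stands, and it is why the size of the loss cannot be fixed from the documents. It does not make 750 the expected analysed number.

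Finally, the study is exploratory, with no success threshold, and the interval on the actual denominator will be reported. That also stands, and it keeps the point minor.

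**Conclusion.** The point holds as a small correction to a stated figure. At n = 750 the worst case is 3.64%, so about 3.6% is accurate and a claim to be better than that is not. The primary NEDA analysis is expected to include fewer than 750 patients, unless enrolment overshoots or almost nobody meets the exclusion rule. Precision will then be slightly worse than stated: over an assumed 0% to 20% exclusion, by at most 4.08 − 3.64 = 0.44 percentage points at a 50% rate and 3.74 − 3.34 = 0.40 at a 30% rate.

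Three stronger readings are not supported. The trial is not shown to miss its precision in general: near the 30% planning rate the half-width stays under 3.6% until about 13.6% are excluded, although 3.3% drifts to 3.4% or 3.5% with 5% to 10% excluded. NEDA precision is not the only basis given for the size of the trial, because the same section cites relapse-rate precision, and that endpoint is analysed on the ITT population (SAP 4.4.2.5). And no particular loss, such as 10%, can be read from the documents. Whether the exclusion rule shifts the NEDA estimate itself is a separate question.

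**What to change.** In SAP 2.3, state that the half-width is about 3.3% at a NEDA rate of 30% and about 3.6% (3.64%) at 50% if all 750 patients are evaluable for the primary analysis. Add one sentence with half-widths for an assumed range of exclusions, labelled as an assumption (at 30% / at 50%): 5% excluded, 3.4% / 3.7%; 10% excluded, 3.5% / 3.8%; 15% excluded, 3.6% / 4.0%. Carry the same wording into Protocol 6.1 and the synopsis, including its copy in SAP Appendix 1, when those are next amended.

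Enrolment, endpoint and method stay as they are. The cost is a sentence or two and a slightly less favourable stated figure.
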